1 INTRODUCTION

Prostate cancer is a major public health problem in Sweden, where it is the most common male cancer and the most common cause of cancer-related death. Each year, approximately 2,500 men die from prostate cancer, accounting for 5% of all causes of deaths among Swedish males. Without early detection, prostate cancer is typically diagnosed at a late stage when curative treatment is no longer an option. Early detection of prostate cancer was made possible by the introduction of the blood test prostate-specific-antigen (PSA) in the early 80's [1]. In some countries, regular PSA-testing is advocated, whereas Swedish authorities and the Swedish National Board of Health and Welfare have long had restrictive attitudes towards general prostate cancer screening, with the concern that it does more harm than good.

1.1 Background and rationale

Curative treatment for localized PC is effective [1, 2] and prostate-specific antigen (PSA) testing can enable the detection of prostate cancer (PC) at an early, curable stage [3-5]. The main problem with PSA-testing is overdiagnosis and the subsequent risk of overtreatment [6-8]. Due to the low specificity of the PSA-test many men are subjected to unnecessary biopsies with associated discomfort and risk of side-effects such as infections and bleeding [9, 10]. The use of systematic biopsy technique, which was the standard clinical method until recently, together with the large number of slow-growing cancers in the prostate never causing harm, are the main mechanisms behind overdiagnosis [11, 12].

Reduction of PC mortality by regular PSA-testing has been convincingly demonstrated [13-15]. However, the beneficial mortality reduction is not presently considered to outweigh the harms of screening. A refined screening strategy that maintains the PC mortality reduction while avoiding unnecessary biopsies and detection of clinically insignificant cancers, is much needed. In recent years, there has been a fundamental shift in the diagnostic work up of men with clinical suspicion of PC with magnetic resonance imaging (MRI) performed before prostate biopsy to guide, and sometimes even omit, biopsy [16]. MRI of the prostate is intended to discriminate insignificant cancers from harmful ones, and in this manner avoid unnecessary biopsies and overdiagnosis [17-19]. The findings of the PRECISION study, and several others, confirmed this and led to the recent paradigm shift in patients with clinical suspicion of cancer [20-23].

In a pilot study embedded within the last screening round of the Göteborg-1 trial, we evaluated prebiopsy MRI in a screening setting with promising results; MRI-targeted biopsy detected almost as many clinically significant cancers as the strategy with systematic biopsy, while reducing the detection rate of insignificant cancers [24]. However, the role of MRI as a screening tool has not yet been documented in large-scale, randomized screening trials. To bring clarity to this matter we launched the "Göteborg-2 trial" in 2015, as a prospective, randomized, population-based trial of PC screening with PSA testing followed by prostate MRI. Herein, we describe the study design, procedures and the analysis plan.

[24]

2 STUDY OBJECTIVES AND OUTCOME MEASURES

This study design can be looked upon as an umbrella evaluating three major research questions: i) will omitting systematic biopsies in all men with elevated PSA (≥ 3 ng/mL) and instead only biopsy MRI positive men, and only so with targeted biopsies, reduce the risk of detecting clinically insignificant cancers while still maintaining a sufficiently high detection rate of clinically significant cancers

ii) Will changing the PSA cut off from 3 ng/ml to 1.8 ng/ml decrease the risk of being detected with advanced, incurable cancer, instead allowing the cancer to be detected at an earlier, curable stage.

iii) Is a screening algorithm including prebiopsy MRI efficient to reduce prostate cancer mortality compared to the mortality in men randomized to a non-invited control group

2.1 Primary objectives

The primary objective of the trial is to evaluate whether changing the screening algorithm in men with PSA ≥ 3 ng/mL from systematic biopsy to MRI-targeted biopsy only, can reduce the risk of detecting clinically insignificant cancers.

2.2 Secondary objectives

1. To evaluate whether screening with pre-biopsy MRI and only MRI-targeted biopsy in men with PSA ≥ 3 ng/mL can maintain the detection rate of clinically significant cancer compared to systematic biopsy.

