3 STUDY DESIGN

This is a population-based screening trial with randomization of men into either controls (not invited) or an intervention group invited for screening. Participating men are further randomly allocated into one out of three test arms with different designs following the flow chart in Figure 1. The rationale for randomizing participating men into three groups is based on the main obstacle with current gold standard, i.e. PSA and systematic biopsies which lead to an unacceptably high rate of over-diagnosis of small indolent cancers.

The hypothesis is that switching from systematic biopsies in all men with elevated PSA to targeted biopsies only, and only in men with positive MRI, will strongly decrease the risk of over-diagnosis and thus shift the balance between benefits versus harms so that screening for prostate cancer could be accepted as general health policy. The design is appropriate for testing this hypothesis and will hopefully provide level I evidence as to the preferred screening algorithm incorporating MRI as an adjunct to PSA as compared to the current gold standard, i.e. PSA and systematic biopsies. Performing systematic biopsies blinded to MRI result and thereafter targeted biopsies in arm 1 (see below) makes it possible i) to compare cancers detected by targeted biopsies only with ii) those detected by the combination of systematic and targeted biopsies and iii) those detected by systematic biopsies only. Hence the following comparisons between different diagnostic approaches can be performed after completion of screening round 1:

- Pre-biopsy MRI and MRI-targeted biopsy only vs systematic biopsy and in case of a positive MRI also targeted biopsy (Arm 2-3 vs Arm1 (primary objective); can also be compared within Arm1)
- Pre-biopsy MRI and MRI-targeted biopsy vs systematic biopsy (Arm 2-3 vs Arm1; can also be compared within Arm1)
- Pre-biopsy MRI and systematic biopsy and in case of a positive MRI also targeted biopsy vs systematic biopsy (Within Arm1)
- Pre-biopsy MRI and in case of a positive MRI both targeted biopsy and systematic biopsy vs systematic biopsy (Within Arm1)
- Pre-biopsy MRI and in case of a positive MRI both targeted biopsy and systematic biopsy vs systematic biopsy and in case of a positive MRI also targeted biopsy (Within Arm1)
- Pre-biopsy MRI and in case of a positive MRI both targeted biopsy and systematic biopsy vs pre-biopsy MRI and MRI-targeted biopsy (Within Arm1)

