6.2 Analysis plan for the primary and secondary endpoints

6.2.1 Primary objective (Detection of insignificant cancer)

- Hypothesis

The proportion of men with insignificant cancer detected by PSA testing with threshold 3 ng/mL, systematic biopsies and MRI-targeted biopsies (p_1) will be different from the proportion detected when omitting systematic biopsies (p_2):

H_0 (null hypothesis): $p_1 = p_2$

H_A (alternative hypothesis): $p_1 \neq p_2$

Although the hypothesis of the investigators is one-sided, that MRI-targeted biopsies only will lower the proportion, the test is two-sided to allow for a significant effect in both directions.

- Analysis populations

First assessment (after completion of screening round 1): All men in arm 1 will be compared to all men in arm 2 and 3 combined. However, for men in arm 3, cancers detected in men with PSA < 3 ng/mL will be ignored.

Later assessments: the analysis will compare all men in arm 1 with all men in arm 2.

The analyses will primarily be carried out according to the intention to treat (ITT) principle, which here means that all men will be included in the analysis and belong to the arm they were allocated to, irrespective of whether they completed the intended diagnostic pathway with MRI and biopsies or not.

Furthermore, per protocol analyses will be carried out including only men who strictly follow the protocol.

An additional analyses will compare men in arm 1 who underwent MRI followed by systematic and possible targeted biopsies (if MRI positive) with those in arm 2 and 3 who underwent MRI and also targeted biopsies but ignoring results from possible systematic biopsies if those were taken at the primary biopsy and the targeted biopsies were benign.

- Analysis

Outcome measure is the relative difference of the proportion of insignificant cancers detected in arms 2 and 3 combined vs arm 1 (the cancers detected in men with PSA below 3 ng/mL in arm 3 will be ignored). In later assessments only arm 1 and 2 will be included. The result will be presented as a point estimate with a two-sided 95% confidence interval, and a p-value of the hypothesis test. Significance testing will only be carried out for the first definition of insignificant cancer (Gleason grade 3+3). The score method will be used for testing and confidence intervals (27). A p-value below 5% will be considered statistically significant.

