6.2.2 Secondary objective (Detection of significant cancer)

The detection of significant cancers will be analysed in the same way as the detection of insignificant cancers except that no hypothesis testing will be performed.

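### Objectives 2.1 and 2.2 name systematic biopsy as comparator, but section 6.2 scores arm 1 on systematic plus MRI-targeted cores, and the systematic-only contrast listed in section 3 is not assigned to objective 2.2

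*Protocol*

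**What the plan says.** **Objectives.** Section 2.1 describes a change "from systematic biopsy to MRI-targeted biopsy only, can reduce the risk of detecting clinically insignificant cancers". Section 2.2 asks whether the new pathway "can maintain the detection rate of clinically significant cancer compared to systematic biopsy". Section 3 promises evidence on MRI as an adjunct to PSA "as compared to the current gold standard, i.e. PSA and systematic biopsies".

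**Analysis.** In section 6.2.1 the reference proportion is the one "detected by PSA testing with threshold 3 ng/mL, systematic biopsies and MRI-targeted biopsies (p_1"), set against the proportion found when systematic cores are left out. Section 6.2.2 says significant cancer "will be analysed in the same way as the detection of insignificant cancers", but without a hypothesis test. The biopsy reference table in section 5.1 scores MRI-positive men in arm 1 on 12 systematic plus 3-4 targeted cores. The additional analysis in 6.2.1 also lets the targeted cores count in arm 1.

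**Design section.** Section 3 lists two separate round 1 contrasts between the arms. One has as its reference "systematic biopsy and in case of a positive MRI also targeted biopsy (Arm 2-3 vs Arm1 (primary objective"). The other is "Pre-biopsy MRI and MRI-targeted biopsy vs systematic biopsy (Arm 2-3 vs Arm1; can also be compared within Arm1"). After several rounds, section 3 lists only the combined reference for this question.

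**The concern.** The objective and the analysis use different comparators. Systematic biopsy alone is the screening practice that the trial hopes to replace. Arm 1 scored on all its cores is a combined strategy that already includes MRI targeting.

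This matters most for the secondary outcome. Section 6.2.2 provides no test and the protocol states no margin, so the reading of whether detection is maintained rests on the estimate and its interval. If that ratio falls below 1, it could be reported as significant cancers lost relative to current screening. The ratio would in fact show only that targeted-only biopsy finds fewer than the combined strategy, which 2.2 does not name.

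**Working it through.** **1. The plan's own figure.** Section 6.1 assumes 9% insignificant cancer among men with PSA ≥ 3 ng/mL in arm 1, halved to 4.5%, with two-sided 5% significance and 80% power. With 1:2 allocation (arm 1 vs arms 2+3):

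- Pooled proportion: (0.09 + 2 × 0.045)/3 = 0.06.
- n in arm 1 = [1.960·√(1.5 × 0.06 × 0.94) + 0.8416·√(0.09 × 0.91 + 0.045 × 0.955/2)]² / 0.045² ≈ 349, rounded up to 350, or 1,050 in total.
- With continuity correction: 382 in arm 1 and 1,146 in total, within 2% of the stated 1,164.
- 1,164/(0.07 × 0.50) = 33,257, against the stated 33,260.

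The sample size therefore reproduces. It is tied to a rate stated for arm 1, not for systematic biopsy alone.

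**2. Direction for significant cancer.** Let S be the arm 1 proportion with Gleason score above 6 on systematic cores, C the proportion on all cores, and T the proportion in arms 2+3. Further cores can find or upgrade a cancer, but they cannot take a man out of the class above 6. Hence C = S(1 + a) with a ≥ 0, and

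T/C = (T/S)/(1 + a) ≤ T/S.

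The planned ratio T/C equals or understates the ratio T/S that 2.2 asks about. If T/C is maintained, T/S is maintained too. If T/C is below 1, T/S may lie on either side of 1.

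**3. Size.** The documents give no value for a. Taking 5 to 25% as an assumption:

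| T/S (question in 2.2) | T/C, a = 5% | T/C, a = 25% |
|---|---|---|
| 1.00 | 1.00/1.05 = 0.95 | 1.00/1.25 = 0.80 |
| 0.95 | 0.95/1.05 = 0.90 | 0.95/1.25 = 0.76 |

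Read the other way, let g = a/(1 + a) be the share of arm 1 significant cancers that only the targeted cores reveal. Then T/S = (T/C)/(1 − g). An observed T/C of 0.90 corresponds to T/S of 0.95, 1.00 or 1.125 for g = 5, 10 or 20%.

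**4. Insignificant cancer.** Here the direction is not fixed. Targeted cores can add men with Gleason 6, and they can also upgrade men out of Gleason 6. If they only add, with a share f of the arm 1 cases found by targeted cores alone and arms 2+3 held at 4.5%, the systematic-only reference is 9% × (1 − f). For f = 0, 5, 10 and 20% the ratio is 0.50, 0.53, 0.56 and 0.63. Power with 388 vs 776 men (1,164 split 1:2, no continuity correction) is 84, 77, 69 and 49%. If upgrading dominates, the shift goes the other way. This is a reason to leave the powered primary test on its present reference.

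**5. Which cores would count.** Two rules affect a systematic-only estimate:

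- *Arms 2 and 3.* Section 5.1 counts completion systematic cores, if taken within one year, in men whose cancer was found by targeted biopsy. Scoring arm 1 on systematic cores alone while keeping these would grade arms 2+3 on more cores and favour them.
- *Arm 1.* Section 4.1 has the systematic cores taken blinded to the MRI result. Section 5.2 designates one targeted core as systematic when the lesion lies in a sector that the systematic set covers. Under section 5.2, the set labelled systematic is not fully MRI-blinded.

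**The case against.** Much of the other side's case stands. Section 3 expressly links the combined reference to the primary objective and lists the systematic-only contrast separately. It also explains that arm 1 takes its systematic cores first so that the strategies can be separated. Question (i) in section 2 is framed around leaving out systematic biopsies, which is the contrast in 6.2.1. The secondary outcome has no test, so no formal decision can be distorted. The combined reference is the stricter one for significant cancer, so a favourable result is safe. A statistical analysis plan that is not at hand may give the details of the section 3 contrast.

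A reader might infer that the trial cannot say whether targeted biopsy maintains the detection of systematic screening, or that the secondary result is biased against MRI. The documents do not support either reading. The contrast is listed, the round 1 design can supply it, and 6.2.1 states its reference openly. The planned ratio is a valid estimate against a different, stricter comparator. A reader might also infer that the all-cores reference lowers the count of insignificant cancers in arm 1, but step 4 shows that the direction is open.

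The mismatch inside the protocol remains. No analysis in section 6.2 uses the comparator that 2.2 names, and only one of the two listed contrasts reaches that section. The objection about core counting is also right, and any systematic-only estimate needs matching rules on both sides.

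**Conclusion.** The point holds as a mismatch of comparators that should be corrected. It is not a flaw in the primary test. For significant cancer under the first definition, the planned ratio can only equal or understate the ratio against systematic biopsy. A maintained ratio answers 2.2, while a shortfall leaves 2.2 open unless the section 3 contrast is run.

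The direction rests on one premise: extra cores do not remove a Gleason score above 6. The size rests on an assumed 5 to 25% gain from targeted cores, for which the documents give no figure. In that range, true equality would show as 0.95 to 0.80. For insignificant cancer, neither the direction nor the size can be settled from the documents.

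**What to change.** - **Section 2.1:** leave the primary test as it is, and name its reference as systematic plus MRI-targeted biopsy.
- **Section 6.2.2:** for round 1, report the arm 2+3 vs arm 1 ratio with arm 1 scored on its systematic cores only, beside the all-cores ratio. Base any statement about systematic biopsy or current standard screening on the systematic-only ratio.
- **Core rules, arms 2 and 3:** for this estimate, grade on the diagnostic cores of the first session, without the later completion systematic cores of section 5.1, or show the result both ways.
- **Core rules, arm 1:** reconcile section 4.1 (MRI-blinded systematic cores) with section 5.2 (one targeted core counted as systematic). Add a sensitivity analysis that excludes that core if it can be identified.

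**Cost:** wording in three sections and one further estimate. Section 5.1 has each cancer-bearing core reviewed separately, so no new procedures are needed. The downside is that two estimates of the secondary outcome must be presented and explained, and the systematic-only one is only as clean as the core labels allow.

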2.3 Additional objectives

1. To evaluate whether detection of clinically significant PC in a curable stage can be improved in screening with pre-biopsy MRI and only MRI-targeted biopsy if the PSA-cut off is lowered from 3 to 1.8 ng/mL. This study will also be described in details in a separate addendum to this protocol
2. To evaluate whether organized sequential screening with PSA followed by MRI can reduce prostate cancer mortality compared to the mortality in men randomized to a non-invited control group. This study will also be described in details in a separate addendum to this protocol.
3. To evaluate whether bi-parametric MRI is non-inferior to multi-parametric MRI in the detection of prostate cancer in a screening setting. This study will also be described in details in a separate addendum to this protocol (26).

2.4 Substudy objectives

A number of side-studies embedded within this trial will be performed evaluating technical aspects of multiparametric MRI (mpMRI) including the role of artificial intelligence, feasibility, logistics, costs, cost- effectiveness, quality of life, biomarkers, equitable care and health care disparities.

2.5 Outcome measures and times of assessments

Details of all outcome definitions and times of assessments are defined in table below.

Outcome definitions and times of assessments for the primary and secondary objectives

Objective	Definition	Time of assessment
Primary	Proportions of clinically insignificant cancers* Arm 1 vs Arm 2+3*	After completion of screening-round 1 (only screening visits in round 1 are analysed). Next assessment includes all screening visits up to 30 th June 2022 and 2, 6 and 10 years thereafter
Secondary	Proportions of clinically significant cancers* Arm 1 vs Arm 2+3*.	After completion of screening-round 1 (only screening visits in round 1 are analysed). Next assessment includes all screening visits up to 30 th June 2022 and 2, 6 and 10 years thereafter
Additional 1)	Proportions of clinically significant cancers Arm 2 vs Arm 3. See separate protocol	Including men who were invited and participated up to 30 th June 2024 and 2, 6 and 10 years thereafter
Additional 2)	Cancer-specific incidence and mortality SG vs CG (intention to screen analysis). See separate protocol	12 years after randomization (31 December 2027) and every third year after.
Additional 3)	Sensitivity and specificity comparing multi- versus bi-parametric MRI. See separate protocol	After completion of screening round 1

SR = screening round. SG = Screening group. CG = control group

* The first analysis based upon screening round 1 will also include men in arm 3 ignoring cancers detected in the PSA range 1.8-2.99 and group them together with men in arm 2, but analysis coming after that including also subsequent screening rounds will only compare arm1 versus arm 2.

The primary definition of clinically significant PC is Gleason¹ Score $\geq 3 + 4$ (also known as Grade Group 2-5) on biopsy but will also be analyzed with other definitions provided in Table page 25.

¹ Gleason grading (after Donald F Gleason 1920-2008) is the pathological grading of prostate needle biopsies. Gleason Score is based on recognizing the two most common morphological Gleason grade/pattern under the microscope, a primary and secondary grade, and then summing the two, e.g. 4+3=7. If there are more than two patterns present, and the worst grade is neither the primary nor the secondary grade, GS is based on the predominant + highest grade. The higher the score, the more aggressive the tumor is.

3 STUDY DESIGN

This is a population-based screening trial with randomization of men into either controls (not invited) or an intervention group invited for screening. Participating men are further randomly allocated into one out of three test arms with different designs following the flow chart in Figure 1. The rationale for randomizing participating men into three groups is based on the main obstacle with current gold standard, i.e. PSA and systematic biopsies which lead to an unacceptably high rate of over-diagnosis of small indolent cancers.

The hypothesis is that switching from systematic biopsies in all men with elevated PSA to targeted biopsies only, and only in men with positive MRI, will strongly decrease the risk of over-diagnosis and thus shift the balance between benefits versus harms so that screening for prostate cancer could be accepted as general health policy. The design is appropriate for testing this hypothesis and will hopefully provide level I evidence as to the preferred screening algorithm incorporating MRI as an adjunct to PSA as compared to the current gold standard, i.e. PSA and systematic biopsies. Performing systematic biopsies blinded to MRI result and thereafter targeted biopsies in arm 1 (see below) makes it possible i) to compare cancers detected by targeted biopsies only with ii) those detected by the combination of systematic and targeted biopsies and iii) those detected by systematic biopsies only. Hence the following comparisons between different diagnostic approaches can be performed after completion of screening round 1:

- Pre-biopsy MRI and MRI-targeted biopsy only vs systematic biopsy and in case of a positive MRI also targeted biopsy (Arm 2-3 vs Arm1 (primary objective); can also be compared within Arm1)
- Pre-biopsy MRI and MRI-targeted biopsy vs systematic biopsy (Arm 2-3 vs Arm1; can also be compared within Arm1)
- Pre-biopsy MRI and systematic biopsy and in case of a positive MRI also targeted biopsy vs systematic biopsy (Within Arm1)
- Pre-biopsy MRI and in case of a positive MRI both targeted biopsy and systematic biopsy vs systematic biopsy (Within Arm1)
- Pre-biopsy MRI and in case of a positive MRI both targeted biopsy and systematic biopsy vs systematic biopsy and in case of a positive MRI also targeted biopsy (Within Arm1)
- Pre-biopsy MRI and in case of a positive MRI both targeted biopsy and systematic biopsy vs pre-biopsy MRI and MRI-targeted biopsy (Within Arm1)

After completion of multiple screening rounds

- Pre-biopsy MRI and MRI targeted biopsy only versus systematic biopsy and in case of a positive MRI also targeted biopsy (Arm 2 versus Arm 1)
- Changing PSA cut off from 3 to 1.8 ng/mL (Arm 2 versus Arm 3)

